6.1. Cluster Inclusion Criteria

Health facilities (clusters) are eligible for inclusion if they have 1000 to 5000 births a year and provide comprehensive obstetric care with ability to perform surgery for PPH. Clusters are selected based on being administratively and geographically distinct from each other. Pre-existing implementation of early detection or bundled approach for PPH management are exclusion criteria.

The cluster start date for inclusion in the study, is the date in which $\geq 80\%$ of their patients have source data verification.

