7.4. Primary outcome analysis

The model being fitted to the binary primary composite outcome will be a mixed-effect logistic regression model with robust standard errors.

To account for clustering, random effects (for cluster and cluster-period) are included (see section 7.4.1). We will account for the time-period using fixed-effects (see section 7.4.2), and will adjust for covariates used in the randomisation in the first instance (see section 7.4.3). If there are issues with model-convergence, then a plan is in place (see section 7.4.4).

Risk ratios and risk differences will then be derived using marginal standardisation [10], as in for example a CRT by Kirkwood et al [11]. Under this approach, the mean risk under the control condition and intervention condition is obtained. The risk ratio is then derived using the mean risk in intervention condition and by the mean risk in the control condition, with the calculation

being performed on the log scale. The risk difference is derived as the mean risk in intervention condition minus the mean risk in the control condition. We will use the unconditional standard errors to obtain the confidence interval, as this allows for correlation amongst the observations [12].

A small sample correction will not be included in the main analyses as the number of clusters is expected to be sufficiently large to maintain the type I error rate [13].

The integration method used will be mean-variance adaptive Gauss-Hermite quadrature, which is the default in Stata.

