7.4.1. Accounting for clustering of observations

To allow for correlation between observations within a cluster, we will fit mixed-effect logistic regression models with robust standard errors. Clustering will be allowed for in all analyses through the use of random effects. Recent developments in the methodological literature for the design and analysis of multiple-period cluster randomised trials suggest that a simple exchangeable correlation structure is not sufficient to depict the correlation structure in multiple-period cluster randomised trials [8]. We will include a random cluster by period interaction in addition to a random cluster effect to allow for the decay in correlation between observations made in the same cluster, but at different time periods.

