7.4.4. Primary outcome - model non-convergence

If the mixed-effect logistic regression model with random cluster and cluster-period effects does not converge, we will remove the cluster-period random effects and fit a mixed-effects model with a random effect for cluster.

If this model does not converge, then we will perform a cluster-level analysis weighted by cluster size to ensure we are targeting the participant-level effect [9]. To perform a cluster-level analysis, for each outcome and for each cluster we will calculate a cluster-level summary statistic for the baseline period and for the post-randomisation period separately. The cluster-level summary statistic will be the proportion of the cluster who experience the outcome.

The data will then be transformed from long format to wide format. That is, instead of having two observations per cluster (one observation that describes the summary statistic during the baseline period and one observation that describes the summary statistics during the post-randomisation phase), each cluster will have one row of data.

Relative risk

To obtain a relative risk, we will fit a linear regression model to a transformed cluster-level summary statistic (log transformation) with a fixed effect for allocated exposure to E-MOTIVE and a fixed-effect for baseline summary measure. We will take the exponential of the covariate related to allocated exposure to E-MOTIVE to obtain the relative risk and 95% confidence intervals. We will use the unconditional standard errors to obtain the confidence interval, as this allows for correlation amongst the observations [12].

Risk difference

To obtain the risk difference, a linear regression model will be fitted to the cluster-level proportions with a fixed-effect for allocated exposure to E-MOTIVE and a fixed-effect for baseline summary measure. We will use the unconditional standard errors to obtain the confidence interval, as this allows for correlation amongst the observations [12].

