As agreed in the DMC charter, at the 3rd DMC meeting (after approximately 75% of births), the DMC will be asked to consider whether there is any clear evidence of substantial selection bias. In the unlikely event that substantial selection bias is confidently identified, then the TSC and TMG will consider whether the sensitivity analysis (with PS) will become the primary analysis for all outcomes. Any decision will be documented in the meeting minutes.

Accounting for missing data

The potential for missing outcome data and missing covariate data is discussed in section 7.7. Below, we present multiple imputation methods to deal with missing outcome and individual-level covariate data. We consider this under two assumptions:

- 1) Data missing is missing at random (MAR)
- 2) Data missing is missing not at random (MNAR).

To evaluate the impact of missing data under MAR and MNAR mechanisms, multiple imputation will be used. We will impute the primary outcome (for all women who do not have source-verified primary outcome data) and individual level covariates (for any covariate used in the adjusted analysis).

Missing at Random

We firstly perform multiple imputation using chained equations [18]. The primary outcome and all covariates required for the adjusted analysis with missing data will be included in the imputation process. The following auxiliary variables will be included to aid the imputation process: country; cluster size (above or below median); Oxytocin quality (high or low); time period (baseline or post-randomisation); exposure to E-MOTIVE; previous C-section; gestational age; antepartum haemorrhage; retained placenta; and non-source verified blood loss.

The number of imputations, n , will be equal to the proportion of patients with any missing primary outcome data. To ensure inferences are valid, clustering will be allowed for in the imputation process. This will be done using BLIMP 3.0 which allow a random effect for cluster to be included [19].

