In each imputed dataset, a propensity score is obtained by fitting a multivariable logistic model with potential confounders (age; parity; multiple pregnancy; mode of birth; and birth weight) in the model, and treatment arm as the outcome. In each imputed dataset, the analysis model with PS included in the model as a covariate is fitted and an estimate of the summary measure is obtained. The RR and RD will be obtained in the same manner as for the primary analysis – using marginal standardisation. The summary measure from each of the n imputed datasets is then pooled using Rubin's rules.

Missing Not at Random

An analysis to assess the effect of missing responses for the primary outcome only. This analysis will explore the possibility that missing responses are 'missing not at random' (MNAR) using a tipping point approach.

We firstly perform multiple imputation using chained equations [18]. The primary outcome and all covariates required for the adjusted analysis with missing data will be included in the imputation process. The following auxiliary variables will be included to aid the imputation process: country; cluster size (above or below median); Oxytocin quality (high or low); time period (baseline or post-randomisation); exposure to E-MOTIVE; previous C-section; gestational age; antepartum haemorrhage; retained placenta; and non-source verified blood loss.

The number of imputations, n , will be equal to the proportion of patients with any missing primary outcome data. To ensure inferences are valid, clustering will be allowed for in the imputation process. This will be done using BLIMP 3.0 which allow a random effect for cluster to be included [19].

For the MNAR mechanism, we will assume the prevalence of the primary outcome differs in those patients with a missing outcome compared to those patients with an observed primary outcome. To do this, we will include a parameter in the imputation process that shifts the expected prevalence (of the primary outcome) by a fixed amount. This "*missing parameter*" is a fixed value, and the magnitude and sign of the coefficient determines the strength and direction of the missing not at random process (see below). This parameter is included in each arm separately, to allow the MNAR mechanism to influence one arm at a time.

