By selecting a variety of values of the missing parameter, we can identify the “tipping point”. This refers to the point in which general conclusion of the primary analysis changes. The tipping point will be determined in one of two ways:

Option A: The CI in the primary analysis does not contain one for the risk ratio (i.e., one treatment is superior to the other), then the point in which the CI crosses one will be highlighted (the tipping point). The base case from the primary analysis will be highlighted.

Option B: The CI in the primary analysis does contains one for the risk ratio (i.e., inconclusive whether one treatment is superior to the other), then the point in which the CI no longer contains one will be highlighted (the tipping point). The base case from the primary analysis will be highlighted.

We will consider two scenarios: MNAR in exposed arm only (i.e., those in E-MOTIVE arm in the post-randomisation period) and MNAR in non-exposed arm only (i.e., those in standard care arm and those in baseline period).

MNAR in exposed arm only

Firstly, we assume that all patients in the unexposed group with missing outcome data have the same prevalence as those who are observed. In the exposed group, we will set the *missing parameter* to change the prevalence of the outcome in those with missing outcome data in the exposed group. We will estimate the effect measure using n imputation, by fitting a model with exposure, time period and cluster-level covariates to each imputed dataset separately. The RR and RD will be obtained in the same manner as for the primary analysis – using marginal standardisation. The summary measure from each of the n imputed datasets is then pooled using Rubin’s rules. The effect measure and CI will be examined and stored. We will use several values of the *missing parameter* to visualise how the effect measures and confidence intervals change as the prevalence of the outcome in those with missing data changes.

MNAR in unexposed arm only

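### The imputation models name a cluster effect but no cluster-by-period effect, so the missing-data sensitivity intervals may be slightly too narrow if the cluster autocorrelation is below 1

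*SAP*

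**What the plan says.** SAP 7.4 specifies the primary model: "To account for clustering, random effects (for cluster and cluster-period) are included". SAP 7.4.1 gives the reason, that "a simple exchangeable correlation structure is not sufficient to depict the correlation structure in multiple-period cluster randomised trials", and continues: "We will include a random cluster by period interaction in addition to a random cluster effect". If that model does not converge, SAP 7.4.4 says "we will remove the cluster-period random effects and fit a mixed-effects model with a random effect for cluster".

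SAP 7.11 imputes the primary outcome for women without source-verified data. In both the missing-at-random (MAR) and the missing-not-at-random (MNAR) parts it says of clustering: "This will be done using BLIMP 3.0 which allow a random effect for cluster to be included". No cluster-by-period term is named. Time period and exposure to E-MOTIVE enter as auxiliary variables, as does non-source-verified blood loss.

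After MAR imputation, "the analysis model with PS included in the model as a covariate is fitted". After MNAR imputation, the effect is estimated "by fitting a model with exposure, time period and cluster-level covariates to each imputed dataset separately", with no mention of random effects. The tipping point is then the value at which the confidence interval for the risk ratio starts to include one (Option A) or ceases to include one (Option B).

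**The concern.** The SAP gives a reason for a cluster-by-period effect in the analysis and then names a simpler structure for the imputation that feeds the same kind of analysis. Period and exposure as fixed terms carry the average shift over time and between arms. They do not carry the extent to which one facility departs from that average in one period. That departure is part of what determines the standard error of the treatment effect in a trial with a baseline and a follow-up period. Imputed women without it dilute it, and the model fitted to the completed data then sees less facility-period variation than there is.

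The affected analyses are those that test whether the primary result survives missing outcomes. The tipping point is read directly from where an interval meets one, so an error in interval width moves it.

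**Working it through.** **1. Inputs from the documents.** ICC 0.018 (95% CI 0.01 to 0.034) from E-MOTIVE baseline data, planning value 0.02; CAC considered from 0.95 to 1.0, with estimates of 0.97 and 0.99 from an earlier trial (SAP 4.7). 192 births per facility per month over 7 months gives m = 192 × 7 = 1,344 births per facility-period. 78 facilities are allocated 1:1, so 39 per arm (SAP 4.3). Baseline prevalence is 3.6%.

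**2. Assumed input.** The missing share f is not stated. I use 5%, 10% and 20%. Protocol 11.2 expects missing data to be minimal. The upper value is prompted by SAP 6.1, where a facility's start date is the date on which at least 80% "of their patients have source data verification". That is an entry criterion, not an expected missing rate.

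**3. Check against the plan's own power table.** Take 72 facilities, ICC 0.02, CAC 0.97, and a fall from 4% to 3%.

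- Size inflated for variation: M = 1,344 × (1 + 0.5²) = 1,680
- 1 + (M − 1) × ICC = 34.58
- r = 1,680 × 0.02 × 0.97 / 34.58 = 0.9425
- Design effect = 34.58 × (1 − r²) = 3.862
- SE = √[(0.04 × 0.96 + 0.03 × 0.97) × 3.862 / (36 × 1,344)] = 0.00232
- z = 0.01 / 0.00232 = 4.31; power = Φ(4.31 − 1.96) = 99.1%

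The table states 99.1%. At 2% prevalence the same steps give 85.5%, also as stated. All 81 cells are reproduced within 1.0 percentage point, so the correlation structure used here is the plan's own.

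**4. Closed form for the narrowing.** In units of the total variance, a facility-period mean has a cluster-period part s = ICC × (1 − CAC) and a within-facility part v = (1 − ICC) / [(1 − f)m]. With cluster-only imputation, a share f of the women carries no facility-period deviation, so the deviation seen in the completed data shrinks by (1 − f) and its variance by (1 − f)². The estimate itself still varies as in the complete cases, because period and exposure are in the imputation model. Hence

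reported SE / true SE = √{[(1 − f)²s + v] / [s + v]}

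For f = 0.20 and CAC 0.97: s = 0.018 × 0.03 = 0.00054; v = 0.982 / 1,075.2 = 0.000913; ratio = √[(0.64 × 0.00054 + 0.000913) / (0.00054 + 0.000913)] = √(0.001259 / 0.001453) = 0.931.

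**5. Simulation.** 39 + 39 facilities of equal size, 1,344 births per facility-period, prevalence 3.6%, 4,000 runs, 20 imputations, Rubin's rules, and an analysis model with cluster and cluster-period effects. The simulated figure is the width of the imputation interval relative to the primary complete-case interval. ICC is 0.018 throughout.

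| CAC | 5% missing: closed form / simulated | 10% | 20% |
|---|---|---|---|
| 1.00 | 1.000 / 1.000 | 1.000 / 1.000 | 1.000 / 0.999 |
| 0.99 | 0.991 / 0.993 | 0.983 / 0.987 | 0.970 / 0.978 |
| 0.97 | 0.980 / 0.982 | 0.961 / 0.966 | 0.931 / 0.939 |
| 0.95 | 0.973 / 0.976 | 0.949 / 0.953 | 0.906 / 0.915 |

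Simulated coverage of the nominal 95% interval at 20% missing is 94.5% (CAC 0.99), 93.2% (0.97) and 92.2% (0.95). With ICC at its upper limit of 0.034 and CAC 0.95, relative width is 0.937 at 10% missing and 0.883 at 20%.

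**6. With the term added.** At 10% and 20% missing, a cluster-by-period effect in the imputation model brings relative width back to 1.00–1.01 for every CAC tried, and coverage to about 94–96%, as in the primary analysis.

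**7. Limits.** The calculation is linear on the proportion scale, with equal facility sizes and equal missingness across facilities. It leaves out the non-source-verified blood loss variable. These runs did not use robust standard errors. A separate simulation that did (ICC 0.02, 20% missing) also found a shortfall, with ratios of 0.907 at CAC 0.95 and 0.912 at 0.97. The second is lower than the closed form at that ICC (about 0.93), so I take only the direction from it.

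**The case against.** The best case for the plan has five parts.

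- **The SAP excludes nothing.** It says the software allows a cluster effect and does not rule out a further term. That is true. Still, an analyst who follows the text as written would fit the structure that 7.4.1 calls insufficient.
- **The relevant CAC may be close to 1.** The protocol ties 0.97 to two 11-month periods and the re-estimate of 0.99 to two 7-month periods, which match the final design. (SAP 4.7 attributes both to 7-month periods.) At 0.99 the narrowing is small. This stands as a limit on size. Both estimates come from another trial, however, and SAP 4.7 says none could be made from the accrued baseline data.
- **Missing data are expected to be minimal.** This also limits the size. A reader might infer a 20% missing share from the 80% start rule, but the documents give no such rate.
- **An auxiliary variable helps.** SAP 7.7 gives two reasons for missingness. Where blood loss was recorded but not verified, that value carries facility-period information, so the real narrowing is probably smaller than the table shows. It cannot help where no blood loss was recorded.
- **The mismatch may not arise.** If the primary model falls back to a cluster effect only, the two structures agree.

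Two stronger readings are tempting. One is that the intervals are too narrow by some 9% whatever the circumstances. That figure needs CAC at the bottom of the plan's range together with 20% missing. The other is that the tipping point always moves further out. That holds under Option A. Under Option B a narrow interval excludes one sooner, so the tipping point is reached slightly too soon.

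**Conclusion.** The inconsistency is in the text and its direction is clear. If CAC is below 1, outcomes are missing and the primary model keeps its cluster-period effect, imputation with the cluster effect alone gives intervals that are somewhat too narrow. Taking closed form and simulation together at ICC 0.018 and an assumed 5–20% missing, the narrowing is about 0% at CAC 1.00, 1–3% at 0.99, 2–7% at 0.97 and 2–9% at 0.95, and probably less where unverified blood loss is available.

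The point is confined to the missing-data sensitivity analyses. A reader might infer that the primary result is in doubt. It is not: the primary analysis uses observed, source-verified data and its own model already has the cluster-period effect. In practice, under Option A the result would look slightly more robust to missing data than it is. This is a minor, inexpensive improvement.

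**What to change.** In SAP 7.11, for both MAR and MNAR, state that the imputation model includes a cluster-by-period random intercept (or a random period coefficient by cluster) in addition to the cluster effect, matching the random effects of the primary model as finally fitted. Also state that the model fitted to each MNAR-imputed dataset uses those same random effects, since the text now lists only its fixed terms.

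The change needs a few lines of imputation code. The costs are longer run time and some risk of non-convergence, for which the fallback in 7.4.4 can be applied: drop the cluster-period effect and report that this was done. Imputing the two periods separately is not a good substitute, because it discards the correlation between periods within a facility.

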7.4.3. Primary outcome – covariate adjustment

In the first instance, the analysis will contain an adjustment for the minimisation parameters listed in section 4.3. Randomisation was performed stratified by country, and so country will also be included as a covariate. However, whilst the number of intervention and control clusters was included in the minimisation, we will not adjust for the number of clusters allocated to E-MOTIVE or usual care.

The number of vaginal births will be modelled as binary (above or below median). Oxytocin quality will be treated as binary (high quality or low quality). Country will be treated as categorical (Kenya, Nigeria, South Africa, or Tanzania).

For the analysis of the primary outcome, we will not include a term for cluster-level primary outcome rate at baseline, as although this was included as a randomisation covariate, the constrained baseline analysis method includes individual-level primary outcome values from the baseline period.

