7.7. Handling missing data

In the first instance, analysis will be completed on received data only with every effort made to follow-up patients to minimise any potential for bias. In E-MOTIVE, there is the potential for missing outcome data and missing covariate data, which is described below. A planned sensitivity analysis using multiple imputation to allow for missing data is described in section 7.11.

Missing outcome data

Primary outcome

Only blood loss data that is source verified is included in the primary analysis of the primary outcome. There are two reasons that a woman could have missing outcome data, (i.e., missing source verified blood loss data): 1) woman has blood loss data recorded but it is not source verified; and 2) woman has no blood loss data recorded on the case report form.

Secondary clinical outcomes

Secondary clinical outcomes may contain some missing data. Blood loss outcomes (blood loss 2 hours postpartum and 24 hours postpartum) and primary PPH may contain missing data for the same reason as the primary outcome. Other outcomes may contain missing information if the case report form containing outcome data has not been completed fully.

Secondary Implementation outcomes

For all implementation outcomes, the case report form denotes whether a woman received the outcome in question. It is assumed if it was not denoted as a “yes” on the case report form that the woman did not receive the outcome. As such, there is no missing data for the implementation outcomes.

Missing covariate data

All cluster-level data included in (unadjusted) primary analysis models (country, oxytocin quality, cluster size) will be complete and not contain any missing information. Country is known for each participant based on their cluster. The quality of Oxytocin has been measured and evaluated for all clusters. The cluster size will be based on the number of patients in the cluster during the baseline period.

Individual data included in the (adjusted) sensitivity analysis models (age; parity; multiple pregnancy; mode of birth; and birth weight) may contain missing data.

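### The SAP's only named missing-at-random analysis adds the propensity score as well as imputing, so a difference from the primary result cannot be attributed to missing data alone

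*SAP*

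**What the plan says.** **Purpose.** SAP 7.11 states: "To evaluate the impact of missing data under MAR and MNAR mechanisms, multiple imputation will be used".

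**Primary analysis.** SAP 7.7 states: "In the first instance, analysis will be completed on received data only". Blood loss without source verification counts as missing. On covariates, SAP 7.4.3 says that "the analysis will contain an adjustment for the minimisation parameters listed in section 4.3". It then adds country and leaves out the count of facilities per arm and the facility's baseline outcome rate. What remains is country, facility size and oxytocin quality. There are no individual-level covariates and no PS.

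**MAR analysis (SAP 7.11).** The outcome and the individual covariates are imputed. A PS is then built in each imputed dataset from "potential confounders (age; parity; multiple pregnancy; mode of birth; and birth weight) in the model, and treatment arm as the outcome". The model is specified as follows: "In each imputed dataset, the analysis model with PS included in the model as a covariate is fitted".

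**MNAR analyses (SAP 7.11).** The imputation set-up is the same, with a shift applied to one exposure group at a time. The effect is then estimated "by fitting a model with exposure, time period and cluster-level covariates to each imputed dataset separately", with no PS. For the tipping-point display: "The base case from the primary analysis will be highlighted".

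**Fully adjusted analysis (SAP 7.11).** This is listed separately. It uses the minimisation factors plus the same PS. The SAP does not name it as the comparator for the MAR result.

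**The concern.** A missing-data sensitivity analysis is easiest to read when it changes one thing, the handling of the missing values. Here the MAR analysis changes two things relative to the primary analysis. If the MAR result differs, the cause may be imputation, individual-level adjustment, or both. If it agrees, two shifts may have cancelled.

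The two families of missing-data analysis also use different outcome models, MAR with the PS and MNAR without it, and no reason is given.

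This matters because missing outcomes are possible by design: a weighed drape without a verified photograph is treated as missing. Protocol 11.2 accepts that leaving such women out carries a risk of bias and relies on sensitivity analyses to assess it. The analysis meant to answer that question should answer it for the primary estimate.

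**Working it through.** No figure in the plan bears directly on this point, so the check sets the specified analyses side by side, separates the two changes, and illustrates them.

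**1. What each analysis uses**

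| Analysis | Outcome data | PS in model | Named in SAP |
|---|---|---|---|
| P: primary | received, verified | no | yes |
| A: fully adjusted | received (reading 7.7 with 7.11) | yes | yes |
| M: MAR | imputed | yes | yes |
| MNAR | imputed, shifted in one group | no | yes |
| I: MAR, primary model | imputed, no shift | no | no |

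**2. Separating the changes (log risk ratio scale)**

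The effect of missing-data handling on the primary estimate is I − P. The SAP names P, A and M.

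- M − P = (I − P) + (M − I): imputation plus PS adjustment.
- M − A = (I − P) + [(M − I) − (A − P)]: equal to I − P only if adding the PS has the same effect on imputed as on received data.

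Neither contrast of named analyses gives I − P in general.

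**3. Illustration**

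From the SAP: outcome risk about 3.6%, a 25% reduction (applied to the odds), risk ratio by marginal standardisation, and PS set to zero at baseline. Assumed: one fully observed prognostic covariate (log odds 0.4 per SD), about 8% missing outcomes, no facility clustering, 5 simple imputations, and 12 runs of 200,000 births. The covariate shift applies to exposed women only. Related missingness means that it depends on the covariate in exposed women. All four estimates in a row come from the same simulated data, so compare within rows.

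| Shift (SD) | Missingness | P | A | I | M | I/P | M/P | M/A |
|---|---|---|---|---|---|---|---|---|
| 0 | unrelated | 0.750 | 0.749 | 0.751 | 0.750 | 1.001 | 1.000 | 1.001 |
| 0 | related | 0.742 | 0.756 | 0.755 | 0.755 | 1.018 | 1.018 | 0.999 |
| 0.1 | unrelated | 0.788 | 0.759 | 0.788 | 0.759 | 1.000 | 0.963 | 1.000 |
| 0.1 | related | 0.759 | 0.745 | 0.774 | 0.745 | 1.020 | 0.982 | 1.000 |
| 0.3 | unrelated | 0.843 | 0.750 | 0.842 | 0.749 | 0.999 | 0.888 | 0.999 |
| 0.3 | related | 0.835 | 0.756 | 0.851 | 0.756 | 1.019 | 0.905 | 1.000 |

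The last three columns are quotients of the risk ratios, for example 0.749/0.843 = 0.888.

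- **No covariate shift:** M/P tracks I/P, so the PS does no harm to the reading.
- **Shift 0.3, unrelated missingness:** M/P is 0.888 although imputation alone does almost nothing (0.999).
- **Shift 0.1, related missingness:** M/P is 0.982 while imputation moves the primary estimate the other way (1.020).
- **M/A stays near 1 in every row**, including the three in which imputation moves the primary estimate by about 2%.

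**The case against.** **The MNAR analyses already isolate missing-data handling.** They impute and then fit primary-type covariates without the PS, and obtain the risk ratio and risk difference as in the primary analysis. At zero shift they would amount to MAR imputation with the primary covariates. This is right. A reader might infer that no missing-data analysis in the SAP differs from the primary by missing-data handling alone, and the MNAR text does not support that. What remains is that the SAP plans several shift values without listing zero, and does not label a zero-shift result as the MAR result.

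**The fully adjusted analysis is a like-for-like comparator.** Primary against fully adjusted shows the effect of adjustment, and fully adjusted against MAR shows the effect of imputation, including recovery of women with missing covariates. This also stands, so it would be too strong to say that the MAR result carries no information about missing data. But the SAP does not name this comparison, and it tests the adjusted estimate rather than the primary one. The M/A column shows that the two can differ.

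**The base case is only a display reference.** The tipping point is defined by where the imputed-data interval crosses one or stops containing it. Highlighting the received-data primary result does not move that point, so the tipping-point method is not invalid on this ground.

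**The PS model may become primary.** SAP 7.11 allows the steering committee and trial management group to consider this if substantial selection bias is confidently identified, an event it calls unlikely. The MAR model would then match the primary, but the MNAR model would not.

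**Conclusion.** The point holds in a limited form. A difference between the primary and MAR results cannot be attributed to missing data alone, and no MAR result for the primary model is named. The primary estimate, its interval and its test are not affected.

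The size cannot be read from the documents. With no covariate imbalance the PS contributes about nothing to the MAR result. With an assumed shift of 0.3 SD in exposed women it accounted for essentially the whole move from 0.843 to 0.749. These figures rest on the assumed covariate strength, shift and missing rate and on the absence of clustering. They are not estimates for this trial.

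A reader might also infer that up to a fifth of women lack a primary outcome, because SAP 6.1 starts a facility once at least 80% of its patients are source verified. That threshold sets a start date. It is neither a missing rate nor a bound on later missingness, and protocol 11.2 expects missing data to be minimal.

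**What to change.** 1. In the MAR-imputed datasets, fit the unchanged primary model: period, exposure, country, facility size, oxytocin quality, and the cluster and cluster-period random effects. Name this the MAR sensitivity analysis.
2. Report the PS model on the same imputations as a separate line, and name the received-data fully adjusted analysis as its comparator.
3. List zero among the MNAR shift values, and show the zero-shift result beside the primary result as the reference in the tipping-point display.

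The cost is a few sentences in SAP 7.11 and one extra model fit per imputed dataset. No new data or imputations are needed.
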